#### **Objectives**

#### **Overall objectives**

Objective 1: To determine whether differential activation in a priori brain regions of interest (ROI) to selected reward and inhibition probes can predict drug use during active treatment.

Hypothesis 1a: Greater activation of a priori limbic ROI (e.g., interconnected amygdala/ventral striatal cluster during brief drug cues; bilateral ventral striatum during reward risk) prior to (FMRI 1) and during (FMRI 2) active treatment will predict greater drug use during the active treatment phase.

Hypothesis 1b. Lower activation of a priori prefrontal inhibitory ROI (e.g., lateral orbitofrontal cortex; supragenual anterior cingulate) during affect-congruent Go-NoGo; inhibition of cue-triggered craving) prior to (FMRI 1) and during (FMRI 2) active treatment will predict greater drug use during the active treatment phase. Objective 2: To determine whether differential activation in a priori brain ROI to selected reward and inhibition probes can predict relapse following active treatment.

Hypothesis 2a: Greater activation of a priori limbic reward ROI (e.g., interconnected amygdala /ventral striatal cluster during brief drug cues; bilateral ventral striatum during reward risk during brief drug cues; reward risk) prior to (FMRI 1), and following (FMRI 3) active treatment will predict greater drug use during the 12-week follow-up period.

Hypothesis 2b: Lower activation of a priori prefrontal inhibitory ROI (e.g., lateral orbitofrontal cortex; supragenual anterior cingulate) during affect-congruent Go-NoGo; inhibition of cue-triggered craving) prior to (FMRI 1) and following (FMRI 3) active treatment will predict greater drug use during the 12 week follow- up period.

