#### Primary outcome variable(s)

For Objective 1: The primary drug use outcome for this objective is illicit-positive urines during the 12 weeks of active treatment (2 Urine Drug Screens per week; 20 total) after FMRI 2.

For Objective 2: The primary drug use outcome for this objective is illicit-positive urines during the 12-week follow-up period (weekly urines; 12 total) after FMRI 3.

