#### **Analysis Plan**

Objective 1: To determine whether differential activation in a priori brain regions of interest (ROI) to selected reward and inhibition probes can predict drug use during active treatment.

For hypothesis 1a, the two brain predictors will be the extracted signal change in the interconnected left amygdala-striatal cluster during the Brief Drug Cues task, and the extracted signal change in the bilateral ventral

striatum in the Balloon Analog Risk Task. For Hypothesis 1b, the predictors will be based on the left amygdala for the Go-NoGO contrast in the Affect-congruent Go-NoGo task, and the dorsal anterior cingulate in the Craving Inhibition task. These measures will be obtained from the fMRI 1 and fMRI 2 scans.

The four brain responses will be analyzed in a similar way. In each case, the responses will be the repeated urine screens obtained during the last ten weeks of treatment. These urine results will be binary, indicating either cocaine use, opiate use, or marijuana use, since the previous test. For each of hypotheses 1a and 1b, we will use mixed effects logistic regression (McCulloch et al, 2008) to relate variation in these responses to a measure of brain activation occurring during one of four tasks. We anticipate that using a random intercept will be sufficient to take account of within-subject correlations across the time points, although more complex covariance structures will be examined. As we are interested in assessing the separate effects of each brain region on the responses, our main analyses will consider the brain regions separately, so Hypotheses 1a and 1b will be addressed by four separate models, with the treatment urines as responses, and one brain predictor as an explanatory variable. These models will be estimated for the fMRI 1 and fMRI 3 scans.

The primary hypotheses will be addressed by the point estimates and tests of significance associated with the regression coefficients for the brain predictors in these analyses. In further analyses, we will examine the joint effects of the brain predictors for the different regions in the same model, and will use model selection based on information criteria (BIC) to determine the simplest model that provides a good fit to the data.

Objective 2: To determine whether differential activation in a priori brain ROI to selected reward and inhibition probes can predict relapse following active treatment.

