Hypothesis 2a: Greater activation of a priori limbic reward ROI (e.g., interconnected amygdala /ventral striatal cluster during brief drug cues; bilateral ventral striatum during reward risk during brief drug cues; reward risk) prior to (FMRI 1), and following (FMRI 3) active treatment will predict greater drug use during the 12-week follow-up period.

Hypothesis 2b: Lower activation of a priori prefrontal inhibitory ROI (e.g., lateral orbitofrontal cortex; supragenual anterior cingulate) during affect-congruent Go-NoGo; inhibition of cue-triggered craving) prior to (FMRI 1) and following (FMRI 3) active treatment will predict greater drug use during the 12 week follow-up period.

The statistical models and analyses for Objective 2 will be very similar to those described above for Objective 1. For these hypotheses, the response will be the urine drug screens obtained in each week of the post-treatment phase. The same brain measures used for Objective 1 will be used, with the distinction that they will be obtained during fMRI 3, following treatment. The same type of mixed effects logistic regression models described above for Objective 1 will be used here also.

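### The Analysis Plan names two scan sets for the Objective 1 predictors, and no single scan numbering fits both to hypotheses 1a and 1b

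*Combined protocol and SAP*

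**What the plan says.** **Schedule (four scans).** The Design section puts fMRI 1 and 2 before treatment starts, fMRI 3 after 2 weeks of treatment and fMRI 4 at the end of treatment. Study Procedures (the part common to all three studies) has the same order, but puts the third scan after 3 weeks, or after 2 weeks for prescription opiates. The compensation section pays for four scans, and the scan-day list runs from Scan Day 1 to Scan Day 4.

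**Objectives and outcomes (three labels).** Hypotheses 1a and 1b refer to activation "prior to (FMRI 1) and during (FMRI 2) active treatment will predict greater drug use during the active treatment phase". Hypothesis 2a refers to activation "prior to (FMRI 1), and following (FMRI 3) active treatment will predict greater drug use", and 2b uses the same labels. The Objective 1 outcome is described as "2 Urine Drug Screens per week; 20 total) after FMRI 2". The Objective 2 outcome is "illicit-positive urines during the 12-week follow-up period (weekly urines; 12 total) after FMRI 3".

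**Analysis Plan, Objective 1.** On the predictors: "These measures will be obtained from the fMRI 1 and fMRI 2 scans". The responses are "the repeated urine screens obtained during the last ten weeks of treatment". The paragraph on the models ends: "These models will be estimated for the fMRI 1 and fMRI 3 scans".

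**Analysis Plan, Objective 2.** The same brain measures are used, "with the distinction that they will be obtained during fMRI 3, following treatment".

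**The concern.** Each primary model relates one brain measure to the urine results, so the choice of scan is the choice of primary predictor. For Objective 1 the plan gives two different scan pairs a few sentences apart. An analyst who follows the text has to pick one, and could do so after seeing the results.

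The term fMRI 3 also changes meaning within the Analysis Plan. It has to be an on-treatment scan for the last Objective 1 sentence to make sense, yet the Objective 2 text says that it follows treatment.

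**Working it through.** **1. Can one numbering satisfy both Objective 1 sentences?** The hypotheses need a scan before and a scan during treatment.

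| Numbering | fMRI 1 and 2 | fMRI 1 and 3 |
|---|---|---|
| Four-scan schedule (Design; Study Procedures) | before, before: no on-treatment scan | before, during: fits |
| Three-scan labels (objectives; outcomes; Objective 2 analysis) | before, during: fits | before, after: cannot predict earlier urines |

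Each sentence fits under one numbering only, and not the same one.

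**2. Where do the labels come from?** Urines are collected twice weekly for 12 weeks.
- After a pre-treatment scan: 2 × 12 = 24.
- After a scan at the end of week 2: 2 × 10 = 20.
- After a scan at the end of week 3: 2 × 9 = 18.

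The plan's 20 urines after FMRI 2, and its ten-week window, are reproduced only if FMRI 2 is an on-treatment scan after week 2. The outcome section therefore uses the three-scan labels, and the 20 is not a separate miscount.

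**3. Objective 2.** The sample-size text expects 144 subjects at the start of follow-up. With about 33% lost by the end of treatment, 216 × 2/3 = 144. This agrees with a post-treatment scan, which the schedule calls fMRI 4.

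**4. Which scan is the baseline?** The documents point both ways.
- Scan 2 looks like an extra session: Imaging Assessments lists potential pilot tasks for Scan Day 2, and cotinine is tested on Scan Days 1, 3 and 4.
- Baseline may be repeated or split: the scan-day list gives Scan Day 2 the Scan Day 1 activities apart from the working-memory index and the anomaly check, and the resting scans are counterbalanced over days 1 and 2.

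**5. Cost of counting only urines after the on-treatment scan.** If that scan follows week 3, the count falls from 20 to 18. With two-sided alpha 0.0125 and 80% power, z = 2.498 + 0.842 = 3.339, and

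detectable OR = exp{ √( 3.339² × [1 + (m − 1)r] / m ÷ [n p(1 − p)] ) },

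where m is urines per subject, r the within-subject correlation (0.3 to 0.5), p the rate of use at the covariate mean and n the number of subjects.

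Check against the plan's Objective 2 range of 1.41 to 2.04, with n = 133 (mean of 144 and 144 × 0.85 = 122) and m = 12:
- p = 0.5, r = 0.3 gives 1.41, the stated lower bound.
- p = 0.2, r = 0.5 gives 1.70, well short of the upper bound.
- p = 0.1, r = 0.5 gives 2.03, essentially the stated 2.04.

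The stated rates are 0.2 to 0.5, but the upper bound is reached only near 0.1, and the incomplete last sentence of the Objective 1 power text mentions 0.1 to 0.9. Both ranges are therefore shown.

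Change from m = 20 to m = 18, with n from 144 to 216 × 0.80 = 173:

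| Case | OR at 20 | OR at 18 | Rise |
|---|---|---|---|
| n = 173, p = 0.5, r = 0.5 (smallest) | 1.4447 | 1.4461 | 0.0014 |
| n = 144, p = 0.2, r = 0.3 (largest for p 0.2 to 0.5) | 1.4958 | 1.4993 | 0.0035 |
| n = 144, p = 0.1, r = 0.3 (largest with p = 0.1) | 1.7107 | 1.7160 | 0.0053 |

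These figures give all subjects 18 urines. Only the cocaine and marijuana cohorts would lose any (216 − 72 = 144 enrolled; about 144 × 0.80 = 115 scanned if the 20% loss applies at that scan), so the true cost is smaller.

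**The case against.** The strongest defence is that the intention can be recovered: scan before, during and after treatment, with the before and during scans predicting use on treatment and the before and after scans predicting use in follow-up. For Objective 2 that defence largely stands. The words say that the scan follows treatment, and the expected 144 subjects agree. A reader might infer that the plan would use a week 2 or 3 scan as its post-treatment predictor, but that requires reading the number and ignoring the words in the same clause. The Objective 2 analysis sentence names only the post-treatment scan, but the hypotheses directly above it also name FMRI 1.

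A reader might also infer that all 20 Objective 1 urines would precede their predictor. That follows only if fMRI 3 is post-treatment in the Objective 1 models, a reading that defeats the hypothesis. It shows that the reading is impossible and is not an expected loss of data.

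It is tempting, too, to settle on scans 1, 3 and 4 as the intended set. The scan-day list and the counterbalanced resting scans do not allow that conclusion.

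The attached schedule and assessment files were not available. They may clarify what each session contains, but they cannot make the two Objective 1 sentences agree.

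**Conclusion.** Wrong as written, and it must be fixed, because the text that selects the Objective 1 primary predictors contradicts itself under either numbering. The cause is three-scan labels left in place beside a four-scan schedule. Objective 2 has a stale label rather than an unclear time point, though fMRI 4 should be named where it is used.

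The conclusion on Objective 1 rests on the text alone. Two points are inferences: that the 20% loss at fMRI 2 in the sample-size text refers to the on-treatment scan, and what fMRI 2 contributes to the baseline. The disagreement over 2 or 3 weeks for fMRI 3 is a minor separate point and does not drive the severity.

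**What to change.** 1. Define each scan once by time point (before, during or after treatment) and relabel the objectives, the primary outcomes and both parts of the Analysis Plan to match. In the sample-size text, state the time point meant by the 20% loss at fMRI 2.
2. Objective 1: name the pre-treatment and on-treatment scans in both sentences. Objective 2: name the pre-treatment and end-of-treatment scans, and anchor the follow-up urines after the latter.
3. The sponsor should state whether the pre-treatment measure comes from fMRI 1, fMRI 2 or both, and if both, how they are combined.
4. Reconcile the Design section and Study Procedures on when fMRI 3 occurs. For the on-treatment-scan models of Objective 1, count only urines collected after that scan and state the resulting number.

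The cost is relabelling. By schedule, at most 2 of 20 urines are lost, in two cohorts and in those models only; a scan done late could lose more. The rise in detectable odds ratio is negligible.

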### The following documents are currently attached to this item:

There are no documents attached for this item.

## Data confidentiality

x Paper-based records will be kept in a secure location and only be accessible to personnel involved in the study.

x Computer-based files will only be made available to personnel involved in the study through the use of access privileges and passwords.

x Prior to access to any study-related information, personnel will be required to sign statements agreeing to protect the security and confidentiality of identifiable information.

x Wherever feasible, identifiers will be removed from study-related information.

x A Certificate of Confidentiality will be obtained, because the research could place the subject at risk of criminal or civil liability or cause damage to the subject's financial standing, employability, or liability. A waiver of documentation of consent is being requested, because the only link between the subject and the study would be the consent document and the primary risk is a breach of confidentiality. (This is not an option for FDA-regulated research.)

Precautions are in place to ensure the data is secure by using passwords and encryption, because the research involves web-based surveys.

# Audio and/or video recordings will be transcribed and then destroyed to eliminate audible identification of subjects

### **Subject Confidentiality**

Every attempt will be made by the investigators to maintain all information collected in this study strictly confidential, unless a subject says he intends to harm himself or another or that he has abused a child or an elderly person. However, authorized representatives of the Sponsor(s) (if any), the University of Pennsylvania, as well as the Food and Drug Administration (FDA), will have access to and may copy, both medical records and records from participation in this study. This access is necessary to insure the accuracy of the findings and subject safety and welfare. If any publication or presentations result from this research, subjects will not be identified by name. The data are kept in secure, locked filing cabinets in locked rooms and access to these areas is possible only through the investigator or research technician. Also, databases are password protected and are on computers that are password protected as well.

4. Subject Privacy/Protected Health Information The following personal health information will be collected, used for research and may be disclosed or released during subjects involvement with this research study:

- Name
- Address
- Telephone number
- Date of Birth
- Social Security Number
- Mother's and Father's name
- Medical Record Number
- Billing Code, date and time
- Family medical history
- Allergies
- Current and past medications or therapies

- Information from a physical examination that generally also includes blood pressure reading, heart rate, breathing rate and temperature

- List all other tests and procedures that will be performed in the study: A complete psychiatric and medical exam with routine labs, a series of interviews and associated forms, questionnaires, MRI scans, urine samples, talk downs with a licensed therapist, therapy for 12 weeks, employment, medical, substance abuse, family/ social, legal, and psychiatric histories, and Neurobehavioral tasks.

As stated above every attempt will be made by the investigators to maintain all information collected in this study strictly confidential, unless a subject says he intends to harm oneself or another or that he has abused a child or an elderly person. However, authorized representatives of the Sponsor(s) (if any), the University of Pennsylvania, as well as the Food and Drug Administration (FDA), will have access to and may copy, both medical records and records from participation in this study. This access is necessary to insure the accuracy of the findings and subject safety and welfare. If any publication or presentations result from this research, subjects will not be identified by name. The data are kept in secure, locked areas and access to these areas is possible only through the investigator or research technician. All of the study staff that will have access to collected data are listed on section 1 of the application. If a new technician is hired for this study then they will be trained and have access to the data. In addition, the following individuals and University of Pennsylvania organizations may use or disclose subjects' personal health information for this research project:

- The Principal Investigator and the Investigators study team (other University staff associated with the study) - The University of Pennsylvania Institutional Review Boards (the committees charged with overseeing research on human subjects) and University of Pennsylvania Office of Regulatory Affairs

- The University of Pennsylvania Office of Human Research (the office which monitors research studies)

- Authorized members of the University of Pennsylvania and the University of Pennsylvania Health System and School of Medicine workforce who may need to access subjects' information in the performance of their duties (for example: to provide treatment, to ensure integrity of the research, accounting or billing matters, etc.). Those outside the university that may use or disclose subjects' personal health information for this research project: - Government agency and/or their representative: Pennsylvania Department of Health and the FDA When all study data is analyzed, written and disseminated all identifiers will be destroyed. Only de-identified data will be published.

#### **Subject Privacy**

Privacy refers to the person's desire to control access of others to themselves. Privacy concerns people, whereas confidentiality concerns data. Describe the strategies to protect privacy giving consideration to the following: The degree to which privacy can be expected in the proposed research and the safeguards that will be put into place to respect those boundaries. The methods used to identify and contact potential participants. The settings in which an individual will be interacting with an investigator. The privacy guidelines developed by relevant professions, professional associations and scholarly disciplines (e.g., psychiatry, genetic counseling, oral history, anthropology, psychology).

Privacy is of the utmost importance in our lab. Participants are interviewed behind closed doors, screens, testing, physicals, and all other measures are done in a private space behind a closed door. All personnel receive HIPAA and CITI Human Subjects Good Clinical Practice training with emphasis on participant privacy.

Participants are recruited through IRB-approved advertising modalities: word of mouth, fliers, list-serves, as well as Internet and local media advertisements. Patients will also be recruited from the Center for Studies of Addiction Treatment Research Clinic (TRC) at the University of Pennsylvania, at [name], and in response to fliers hung, pamphlets and letters sent to Valley Forge Medical Center and Hospital, Kirkbride Center, Keystone Center, Seabrook Hourse, Physicians, Counseling Centers and like places in order to forge a relationship for reciprocal referrals. In addition to participants recruited by public advertising, we have several additional sources of eligible participants for the project, including the natural flow of treatment-seeking cocaine patients who come to the Center for Studies of Addiction Treatment Research Clinic (TRC) at the University of Pennsylvania, at [name], to the Penn Presbyterian Center, and to the Philadelphia VA Medical Center. These latter sites have longstanding collaborative relationships with our Center, and the VA is a formal collaborator for the CURE project. In order to increase our recruitment effort chances, we plan to advertise/recruit using Google. A Google search for different words like Cocaine, treatment or Philadelphia will connect a person to the Center for Studies of Addictions Department of Psychiatry Penn Behavioral Health web page that lists our current research studies and contact information. We also plan to advertise/recruit from ResearchMatch.org, Facebook, Penn Video Network Video Bulletin Board (and like venues at universities and colleges), at business and other places that allow us, and in newspapers. The name "TreatmentInPhilly.com" was purchased so that we can add this name to currently used and new advertisements because it is a much easier web address to remember then the Center for Studies of Addiction web address (http://www.med.upenn.edu/csa/brain clinicaltrials.html). It is hoped that participants will be able to remember this address that take them directly to our CURE research web page once the connection of these 2 addresses is made by the University of Pennsylvania Center's web page staff.

Individuals will be interacting with investigators in a private closed-door setting (in a lockable office space) and possibly at the MRI scanning session that is located in a close door space with a separate MRI area.

### **Data Disclosure**

Will the data be disclosed to anyone who is not listed under Personnel? No

### **Data Protection\***

- x Name x Street address, city, county, precinct, zip code, and equivalent geocodes
- x All elements of dates (except year) for dates directly related to an individual and all ages over 89
- x Telephone and fax number
- x Electronic mail addresses
- x Social security numbers
- x Medical record numbers
- Health plan ID numbers

Account numbers Certificate/license numbers Vehicle identifiers and serial numbers, including license plate numbers Device identifiers/serial numbers Web addresses (URLs) Internet IP addresses Biometric identifiers, incl. finger and voiceprints Full face photographic images and any comparable images Any other unique identifying number, characteristic, or code None

**Tissue Specimens Obtained as Part of Research\*** Are Tissue Specimens being obtained for research? No

